4.13.2 Delis-Kaplan Executive Function System (D-KEFS)

The D-KEFS⁴¹ is a set of subtests used to assess key components of verbal and non-verbal executive function in children and adults, including flexible thinking, inhibition, problem solving, planning, impulse control, concept formation, abstract thinking, and creativity in both verbal and spatial modalities. We will administer three of the D-KEFS subtests including the verbal-fluency test, colour-word interference test and sorting test. The D-KEFS is administered in a game-like, engaging format in which the researcher provides instructions and feedback throughout. The D-KEFS subtests are administered and scored on a mixture of Q-Interactive and paper. Duration: 30 minutes.

4.13.3 Child and Adolescent Memory Profile (CHAMP)

The CHAMP⁴² is a measure of learning and memory administered among children and adolescents aged 5-21. The CHAMP includes four subtests; verbal memory, visual memory, immediate memory and delayed memory. Subtest scores combine to yield an overall Total Memory Index, with higher scores indicative of better memory performance. The CHAMP is administered and scored on paper. Duration: 35 minutes.

4.13.4 Memory Validity Profile (MVP)

The MVP⁴³ assesses whether a CYP's memory score is a valid estimate of their memory ability. This individually administered test is designed for CYP aged 5-21 and includes two subtests: visual and verbal. The MVP visual and verbal subtest scores combine to yield an MVP Total score, with higher scores indicating greater likelihood of invalid performance. The MVP is administered digitally and scored on paper. Duration: 6 minutes.

4.13.5 Behaviour Rating Inventory of Executive Function (BRIEF)

The BRIEF2^{44, 45} is the second edition of the BRIEF⁴⁵ and is a 63-item parent-reported measure designed to assess executive function in CYP aged 5-18. Each item is scored using a 3-point Likert scale (1= never; 3= often). The BRIEF2 provides 3 index scores: a Behavioural Regulation Index (combining the subscales Inhibit and Self-Monitor), an Emotion Regulation Index (combining the subscales Shift and Self-Monitor). The electronic version of this document is the latest version. It is responsibility of the individual to ensure that any paper material is the current version. Printed material is uncontrolled documentation.

Emotional Control), a Cognitive Regulation Index (combining the subscales Initiate, Working Memory, Plan/Organize, Task-Monitor and Organisation of Materials), and a Global Executive Composite score (combining all 9 subscales). The BRIEF is administered and scored on paper. Duration: 10 minutes.

4.14 Safety Data

4.14.1 Physical Exam

The physical examination will be the standard exam conducted by a qualified physician at screening and repeated at baseline if 3 months has elapsed. The extent of subsequent examinations will be at the discretion of the physician, as clinically indicated. The physician will be adequately experienced and delegated by the PI to undertake Tanner staging assessments. A chaperone will be present throughout any physical examination. Any examinations not required should be recorded as 'not done'.

The physical assessment may include:

- Paediatric physical examination of cardiovascular system, respiratory system and abdomen for general health.
- Height and weight will be recorded.
- Optional body composition assessment using Tanita scales may be used to obtain detailed body mass percentages.
- Routine nursing observations including heart rate, blood pressure, respiratory rate and oxygen saturations

Height should be measured using a stadiometer to the nearest millimetre. Weight should be measured using calibrated scales with the participant in light clothing. If a young person prefers to remain more covered due to body-related distress, this should be noted and considered when interpreting the measurement.

4.14.2 Electrocardiogram (ECG)

A 12-lead ECG will be collected at screening for systemic cardiac monitoring. ECGs will be collected at follow up visits where indicated clinically.

4.14.3 Puberty Staging Assessment (Tanner staging) – Clinical Examination

Tanner staging assessments will be conducted at screening for all TRIAL participants by a qualified, adequately experienced physician, delegated by the PI at each site. For both TRIAL arms, if more than 3 months out of date at the baseline visit, the Tanner staging assessment will be repeated. For immediate group participants, the 12 and 24 month assessments are optional. For those in the delayed start GnRHa arm, there will be a further Tanner stage assessment at 12 months, prior to initiation of intervention – the 24 month assessment is optional. A chaperone will be present throughout the Tanner staging assessment. Chaperones cannot be the CYP's accompanying parent/legal guardian.

The electronic version of this document is the latest version. It is responsibility of the individual to ensure that any paper material is the current version. Printed material is uncontrolled documentation.

4.14.4 Puberty Staging Assessment – Self-Reported

CYP will be presented with a sex-specific pubertal self-assessment questionnaire which includes realistic coloured images⁴⁶ from which they are asked to select the picture that they believe most accurately represents their current stage of pubertal development. Birth registered females will be asked to choose the most appropriate breast and pubic hair Tanner stage. Birth registered males will be asked to choose the most appropriate genital and pubic hair Tanner stage.

Pubertal self-assessment questionnaires completed by TRIAL participants at the baseline, month 12 and month 24 visits. PATHWAYS HORIZON INTENSIVE participants will complete pubertal self-assessment questionnaires at baseline and 24 months.

4.14.5 Vital Signs

Systolic and diastolic blood pressure, weight, height, and BMI centile will be obtained at each visit. Vital signs will be measured in upright position after the participant has been rested for five minutes.

4.14.6 Dual X-Ray Absorptiometry (DEXA) Scan

Hip and spine DEXA Scans will be performed, with the option of whole-body and/or volumetric DEXA scans solely for clinical reasons where deemed clinically indicated by the PI or SI. DEXA scans will be performed at screening, month 12 and month 24 for all TRIAL participants. For HORIZON INTENSIVE, DEXA scans will be performed at baseline and month 24 only.

DEXA scans will assess bone mineral density (BMD); absolute BMD (g/cm²) and age and birth-registered sex standardised Z-scores calculated by machine software will be reported. Scans should be performed on the same scanner and analysed with the same software version throughout the trial. If software changes locally at endocrine centres, preceding scans should be re-run with the new software. In the event the DEXA scanner breaks during the trial, subsequent scans should ideally be taken on a scanner by the same manufacturer.

4.14.7 Bone Age X-Ray

Bone age X-Rays of the left hand/wrist will be performed at screening for all TRIAL participants. Bone age X-Rays will be reported using the Tanner Whitehouse II method. For TRIAL participants the month 12 and 24 scans are optional - bone age X-Rays do not need to be repeated if growth plates are fused. An initial bone age assessment will allow calculation of expected final height and comparison to actual final height can be made. For HORIZON INTENSIVE participants, bone age X-Rays will be performed at baseline only.

4.14.8 Adverse Events

During each visit, participants will be asked about adverse events. All adverse events will be recorded in an ongoing adverse event log. Recording of symptom changes is only necessary when treatment is initiated or when the clinician identifies an unusual rate of change. In the immediate arm, there will be an additional telephone visit led by Clinical Nurse Specialists (CNS) or a delegated medical professional, at 3 and 15 months to ask about adverse events that may require discussion with the PI or SI. A researcher will conduct the telephone visits at 9 and 21 months. Within the delayed arm, there will be a parallel researcher-led telephone visit at 3, 9 and 21 months, with a telephone visit at 15 months led by a CNS or delegated medical professional. All telephone check-ins will follow a standardised proforma with clear guidance on escalation to clinical staff if any concerns arise. This ensures consistency in data collection and participant safety, while allowing flexibility in staffing.

The measures included at each assessment point will assess several adverse events (AE) experienced since the last assessment. Systematic enquiry will include, for birth-registered females, breakthrough menstrual bleeding. All participants will be asked about severe and persistent headaches, galactorrhoea, significant weight changes, unexplained pain, persistent nausea or vomiting, and any other physical symptoms that significantly impact the participant's daily functioning. These physical events will be assessed for their severity and potential relation to the study intervention, and appropriate medical interventions will be provided as necessary.

Follow ups will include suicidal thoughts, suicidal behaviour, a marked increase in the severity of anxiety or depression symptoms, defined as T-score on RCADS subscales >80 when previously lower, increased mental distress requiring unplanned clinical appointments and/or A&E attendances. They will also include detailed information on the child's height and weight, prescribed medications, new diagnoses (both neurodevelopmental and mental health, as well as physical health), and the number of GP appointments attended in the past year. It will also cover any planned surgeries or procedures, A&E visits, reasons for these visits, and whether they led to overnight admissions.

Any hospital admission for an overnight stay will be recorded as a serious adverse event (SAE).

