4.15.1 Safety Bloods

4.15.1.1 *TRIAL Participants*

SCREENING AND BASELINE

All blood tests detailed below will be required at screening and baseline. A serum beta HCG will only be required at baseline to exclude early pregnancy prior to initiation of GnRHa.

Baseline blood tests will usually require anyone on contraceptive treatment (and other hormones as indicated) to have a washout period – where the hormones are not taken – prior to the blood test to ensure true basal hormone panel blood results are interpreted accurately. This will be a clinical decision that takes account of risk of becoming pregnant (and will consider the potential to move to other forms of contraception). The length of washout period is dependent on the type of medication the CYP is using and there may be some circumstances where a washout period is not required. The baseline blood test may need repeating if the washout period needs to be extended to show gonadal axis function. The length of washout period is

to be discussed with and determined by the expert endocrine panel. This panel consists of experienced paediatric endocrinologists from the UK and EU.

Screening blood tests do not require a washout period. Blood tests are to be repeated at the baseline visit if more than 3 months has elapsed since screening.

FOLLOW UP VISITS

At 6-monthly follow-up visits, the following blood tests are mandated: FSH, LH, Oestradiol, Testosterone, Renal Profile, Full Blood Count, Magnesium, Prolactin, Lipid and Bone Profiles. Additional blood tests may be ordered by the PI or SI where clinically indicated. These may include tests outside the standard panel, based on individual participant needs or emerging safety concerns.

HAEMATOLOGY

FULL BLOOD COUNT:

Haemoglobin Platelet count Total and differential leukocyte count
(neutrophils, lymphocytes, monocytes, eosinophils, basophils.) Haematocrit
Red blood cell count

BIOCHEMISTRY

RENAL PROFILE:

Sodium Potassium Creatinine Urea

LIVER PROFILE:

Alanine Transaminase (ALT) Aspartate Aminotransferase (AST) Alkaline
Phosphatase (ALP) Bilirubin Albumin Total Protein

LIPID PROFILE:

Total Cholesterol HDL LDL

BONE PROFILE:

Calcium Phosphate Parathyroid Hormone (PTH)

OTHER:

Ferritin Follicle Stimulating Hormone (FSH) Luteinising Hormone (LH)
Oestradiol Testosterone Prolactin Thyroid Stimulating Hormone
Free T4 Vitamin D

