5.2 Intervention and comparator description, dosing and labelling and intervention

5.2.1 Medication:

The primary intervention all participants will initiate treatment on is Decapeptyl® SR (long-acting formulation of Triptorelin) 22.5mg intramuscular injection (6 monthly preparation).

5.2.2 Labelling:

The information presented on the IMP labels will be annex 13 compliant.

5.2.3 Administration:

The dose of Decapeptyl SR (long-acting formulation of Triptorelin) 22.5mg is administered every six months at 0, 6, 12, 18, and 24 months post-randomisation. This dosing regimen is in adherence to the approved schedule in the Decapeptyl SmPC for the indication of precocious puberty in the same age group, used in routine clinical care. In cases of documented tolerability issues, inadequate suppression of puberty, or product unavailability, alternative regimens may be implemented in accordance with expert panel recommendation and confirmation, as outlined in Appendix C with the following products:

- Decapeptyl® SR (long-acting formulation of Triptorelin) 11.25mg intramuscular injection (3 monthly preparation)
- Prostap 3 DCS (Leuprorelin Acetate) 11.25mg intramuscular injection (3 monthly preparation)
- Gonapeptyl (Triptorelin) 3.75mg intramuscular injection (1 monthly preparation)

5.2.4 Monitoring:

Following administration, participants will be monitored during their clinic visit for any immediate adverse reactions post-injection. The length of the monitoring period is determined by the principal or sub-investigator at the endocrine centre based on their clinical expertise.

Regular follow-up appointments to assess efficacy and safety, including monitoring hormone levels and physical development.

Routine blood tests, DEXA scans, and physical assessments (height, weight, BMI, blood pressure, body composition using Tanita scales if available, and puberty staging).

Psychosocial screening to identify any unmet needs and escalate these to appropriate services.

5.2.5 Fertility Preservation:

Discussion of fertility preservation options with referrals to fertility specialists if desired.

5.2.6 Comparator:

Delayed Start: Participants in the delayed start group will begin GnRHa treatment one year after randomisation. They will receive the same monitoring and assessments as the immediate start group.

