8.6 Treatment Interactions

There are no known drug interactions with Triptorelin or Leuprorelin acetate.

9 Adverse Event Management and Reporting

All adverse events will be recorded in the participant's medical notes, the study source data worksheets and the eCRF. All Adverse Events and Serious Adverse events will be recorded from the signing of the informed consent form until 12 weeks following the final dose. This reporting period reflects the prolonged pharmacological activity of the 6-month Triptorelin formulation. Events suspected to be related to the IMP occurring beyond this window should also be reported.

SAE's will be additionally reported, within 24 hours of site becoming aware of the event, to the KHP-CTO pharmacovigilance team.

All SAEs, SARs and SUSARs (except those specified in this protocol as not requiring reporting) will be reported immediately (and certainly no later than 24hrs) as per the instructions on the SAE report form. SUSARs will be reported prospectively to the chair of the Data Monitoring Committee (DMC); all other safety events will be listed in DMC reports.

The sponsor will report SAEs and/or suspected unexpected serious adverse reactions as required to regulatory authorities, investigators/institutions, and IRBs/IECs in compliance with all reporting requirements according to local regulations and good clinical practice.

The Medicines for Human Use (Clinical Trials) Regulations 2004 and Amended Regulations 2006 gives the following definitions:

- **Adverse Event (AE):** Any untoward medical occurrence in a participant to whom a medicinal product has been administered, including occurrences which are not necessarily caused by or related to that product.

The electronic version of this document is the latest version. It is responsibility of the individual to ensure that any paper material is the current version. Printed material is uncontrolled documentation.

- Adverse Reaction (AR): Any untoward and unintended response in a participant to an investigational medicinal product which is related to any dose administered to that participant.
- Unexpected Adverse Reaction (UAR): An adverse reaction the nature and severity of which is not consistent with the information about the medicinal product in question set out in the SmPC for that product.

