Management of Rare Side Effects: Rare side effects such as anaphylactic reactions, haemorrhage, and idiopathic intracranial hypertension will be monitored closely, and treatment will be discontinued if severe cutaneous adverse reactions (SCARs) occur.

Follow-Up of Adverse Events: All adverse events will be followed until resolution, stabilisation, or until the participant is lost to follow-up. Supplemental investigations may be conducted to elucidate the nature and causality of the adverse events.

11 Premature Termination of Trial

The trial may be prematurely discontinued by the Sponsor, Chief Investigator or Regulatory Authority on the basis of new safety information or for other reasons given by the DMEC, PMC, regulatory authority, or ethics committee concerned.

If the trial is prematurely discontinued, active participants will be informed and no further participant data will be collected. The Competent Authority and Research Ethics Committee will be informed within 15 days of the early termination of the trial.

12 Ethics Approval

This protocol and related documents will be submitted for review to Health Research Authority (HRA), REC and MHRA.

PATHWAYS TRIAL, HORIZON INTENSIVE and CONNECT will be conducted in compliance with the principles of the Declaration of Helsinki (1996), the principles of GCP and all of the applicable regulatory requirements (specify current legislation).

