Trauma (APCTSS)		X				X				X	X ***
Emotional & Behavioural Problems (CBCL, YSR)		X				X				X	X ***
Eating Problems (SCOFF)		X				X				X	X ***
SCANS											
DEXA	X	X				X				X	X ***
Bone Age Scan (X-Ray)	X	X				X^				X^	
CLINICAL MEASURES											
Tanner Staging**	X	X				X				X	
Self-reported puberty staging assessment		X				X				X	
Physical examination	X	X				X		X		X	
***Vital signs	X	X				X		X		X	
ECG	X										
Review of systems (history and examination)		X				X		X		X	
(Optional) Body Composition - Tanita Scale		X				X		X		X	
Telephone check-in			X		X		X		X		
Safety bloods	X	X				X		X		X	

The electronic version of this document is the latest version. It is responsibility of the individual to ensure that any paper material is the current version. Printed material is uncontrolled documentation.

Timepoint/Event	Screening (≤ 12 weeks to Day 0)	Baseline (Day 0)	Month 3 [+/- 2 weeks]	Month 6 [+/- 2 weeks]	Month 9 [+/- 2 weeks]	Month 12 [+/- 4 weeks]	Month 15 [+/- 2 weeks]	Month 18 [+/- 2 weeks]	Month 21 [+/- 6 weeks]	Primary outcome Month 24 [+/- 8 weeks]	Ongoing*
***Pregnancy test (pocbp)++	X	X				X		X		X	
Urinalysis	X	X			X		X			X	
COGNITIVE MEASURES											
General Intelligence – WISC V		X				X				X	
Inhibition, shifting, verbal fluency – D-KEFS		X				X				X	
Memory: visual recognition, verbal recall - CHAMP		X				X				X	
Memory validity profile - MVP		X				X				X	
Executive functions at home - BRIEF		X				X				X	
MAGNETIC RESONANCE IMAGING (PATHWAYS CONNECT)											
Structural/functional Imaging – s/fMRI		X				X				X^^	
ONGOING											
***Adverse events log											X
***Concomitant medications log											X
Withdrawal form											X
PHARMACY											
Study medication dispensing/administration						X	X+++	X	X+++	X	
Study medication dosing log											X

The electronic version of this document is the latest version. It is responsibility of the individual to ensure that any paper material is the current version. Printed material is uncontrolled documentation.

Timepoint/Event	Screening (≤ 12 weeks to Day 0)	Baseline (Day 0)	Month 3	[+/- 2 weeks]	Month 6	[+/- 2 weeks]	Month 9	[+/- 2 weeks]	Month 12	[+/- 4 weeks]	Month 15	[+/- 2 weeks]	Month 18	[+/- 6 weeks]	Month 21	[+/- 2 weeks]	Primary outcome Month 24	[+/- 8 weeks]	Ongoing*
Legend																			

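### Adverse-event ascertainment differs by arm in year 1, and the 12-week recording window and early-termination rule conflict with the protocol's own follow-up

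*Protocol*

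**What the plan says.** **Recording rule.** Section 4.14.8 has participants asked about AEs at every visit, and "All adverse events will be recorded in an ongoing adverse event log". The next sentence is "Recording of symptom changes is only necessary when treatment is initiated or when the clinician identifies an unusual rate of change".

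**Telephone calls.** Both arms are called at months 3, 9, 15 and 21 on one standardised proforma. At month 3 the immediate arm is called by a nurse specialist or delegated medical professional. For the other arm, "Within the delayed arm, there will be a parallel researcher-led telephone visit at 3, 9 and 21 months". Month 15 is clinician-led in both arms.

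**Scheduled tests.** Section 5.2.6 says of the delayed arm: "They will receive the same monitoring and assessments as the immediate start group". Section 4.15.1.1, which covers all TRIAL participants, says: "At 6-monthly follow-up visits, the following blood tests are mandated". In Appendix A, the "Safety bloods" row has a month-6 mark in Table 4 (immediate) and none in Table 5 (delayed). Section 7.1.1 requires abnormal results to be entered as AEs.

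**Window.** Section 9 records AEs and SAEs from consent "until 12 weeks following the final dose. This reporting period reflects the prolonged pharmacological activity of the 6-month Triptorelin formulation". Later events are reportable if suspected to be related to the study drug. Section 5.6 keeps participants who stop treatment on their arm's schedule to the end of the study.

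**Early termination.** Section 11, repeated in 14.2, says: "If the trial is prematurely discontinued, active participants will be informed and no further participant data will be collected".

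**The concern.** Section 2.2 makes the first 12 months the only comparison of GnRHa with no endocrine treatment. Adverse events are a listed outcome (Section 13.1.7), and risk is half of the primary objective. If one arm is examined and tested more often in that year, part of any difference in AE counts reflects how hard each arm was looked at. Staff who ask about and judge events are unblinded (Table 3), so blinding does not protect against this.

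The window and the termination rule raise a different problem: completeness. They decide whether events are recorded at all in participants who stop early, in those never dosed, in the later part of the last dosing interval, and after a stop that may itself have been made for safety. Events not sought at the time cannot be recovered at analysis.

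**Working it through.** **1. Year-1 ascertainment, arm by arm**

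| Element | Immediate | Delayed |
|---|---|---|
| General AE rule, symptom list, call months, proforma | common | common |
| Trigger for recording symptom changes | month 0 | month 12 |
| Month-3 caller | nurse specialist or medical professional | researcher |
| Month-6 examination, vital signs, review of systems, safety bloods, pregnancy test | scheduled (Table 4) | none (Table 5) |
| Safety-blood panels after baseline, to month 12 | 2 (months 6, 12) | 1 (month 12) |

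Some rows of these tables have shifted columns in the extracted text (the Table 5 urinalysis row is one, and was not used). Counting marks per row avoids relying on column position. Table 4 against Table 5 gives 6 against 5 for examination, vital signs, bloods and pregnancy test, and 5 against 4 for review of systems. Each delayed-arm row is one mark short.

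**2. What one extra panel can do (hypothetical)**

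The protocol gives no rate of abnormal results, so the per-panel probability p is an assumption. Assume no drug effect and the same p in both arms. With independent panels, the share with at least one laboratory AE is 1 − (1 − p)² with two panels and p with one. The last column is the chance of a two-sided 5% difference at 113 per arm, from Φ[(d − 1.96·se₀)/se₁], where d is the difference in shares, se₀ the pooled and se₁ the unpooled standard error.

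| p | Two panels | One panel | Ratio | Chance of a spurious signal |
|---|---|---|---|---|
| 5% | 9.75% | 5% | 1.95 | 28% |
| 10% | 19% | 10% | 1.90 | 48% |
| 20% | 36% | 20% | 1.80 | 77% |
| 30% | 51% | 30% | 1.70 | 90% |

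Independence is the extreme case. If the same participants were abnormal at both panels, both shares would equal p and the excess would be zero. The AE threshold also matters: Section 7.1.1 says any abnormal result, whereas Section 4.15 refers to clinically significant ones, which implies a smaller p. The table shows a mechanism and a direction. It does not estimate the bias in this trial.

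**3. The window against the dosing interval**

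Six months is 365.25 / 2 / 7 = 26.1 weeks. Coverage is 12 / 26.1 = 46%, leaving 26.1 − 12 = 14.1 weeks.

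Twelve weeks is 84 / 30.44 = 2.76 months. Read literally, the window closes as follows.

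| Last dose (month) | Window closes (month) | Months of 24-month follow-up outside it |
|---|---|---|
| 0 | 2.8 | 21.2 |
| 6 | 8.8 | 15.2 |
| 12 | 14.8 | 9.2 |
| 18 | 20.8 | 3.2 |
| 24 | 26.8 | 0 |

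A delayed-arm participant who never receives a dose has no final dose, so the closing date is undefined.

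**4. Early termination**

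Section 9 runs AE recording past the last dose, and Section 9.2 follows AEs until resolution, stabilisation, another explanation or loss to follow-up. Sections 11 and 14.2 end all data collection on termination. Both cannot hold for a participant dosed recently, or with an open event, when the trial stops.

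**The case against.** The strongest reply is that the arms share one AE system. Everyone is asked about AEs at each visit, everything is logged from consent, the call months and proforma are the same, and the listed symptoms are asked of all. This stands. A reader might infer that the two arms work under different AE rules throughout; the documents do not say so. The symptom-change sentence names no arm. Its effect on the delayed arm is an inference from the timing of its trigger. The month-3 caller is a minor point: one call of four differs, on a common proforma, and the delayed arm has its own clinician-led call three months after its first scheduled injection.

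Table 2 cannot be set against Table 5 as a contradiction. It is the combined schedule, also marks dispensing at baseline and month 6, and Section 4.2 sends the reader to Appendix A for each arm. The conflict with Sections 5.2.6 and 4.15.1.1 remains.

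A reader might also infer that events late in the last dosing interval are lost. Section 9 keeps suspected-related events reportable beyond the window, and AEs already open are followed up. What stops is routine recording of new events not suspected to be related, and Section 9.2 imposes no duty to seek events in former participants. Nor does the window bias the randomised comparison in completers: both arms are scheduled for a month-24 dose, so it closes after the endpoint and alike in both.

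Finally, the planned binary analysis is a Bayesian logistic mixed model with a 24-month estimand, not a z-test at month 12. The percentages above are illustrative for that reason too.

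**Conclusion.** The point holds as a risk of detection bias in year 1, together with two recording rules that conflict with the rest of the protocol. It does not hold as a demonstrated bias. The month-6 gap in Table 5 is the main evidence, the symptom-change sentence adds to it, and the month-3 caller adds little. The likely direction is more recorded AEs in the immediate arm. The size cannot be computed from the protocol, because it depends on abnormal-result rates, on their persistence between panels and on how sites read the symptom-change sentence.

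The window covers about 46% of the interval used to justify it, leaving about 14 weeks without routine recording of new, unsuspected events. For early stoppers it leaves roughly 3 to 21 months of scheduled follow-up outside it, depending on the last dose, if Section 9 is read literally. The termination rule contradicts Sections 9 and 9.2 outright. These should be corrected before they govern data collection, because missed or unequally sought events cannot be restored later.

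**What to change.** 1. **Section 4.14.8.** Delete or reword the symptom-change sentence so that all AEs are recorded from consent in both arms, whether or not treatment has started. The AE definition in Section 9 refers to participants who have been given a medicinal product, so state that events in the delayed arm before its first dose count.

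2. **Table 5 with Sections 5.2.6 and 4.15.1.1.** Reconcile them. Whether the delayed arm has month-6 tests is for the sponsor to decide. If the difference stays, correct Section 5.2.6 and base the main between-arm AE comparison on events sought identically in both arms. Report events found only through arm-specific tests separately and in full as safety data: dropping them would hide real drug effects, and pooling them would mix in the extra testing. Align the laboratory AE threshold in Sections 4.15 and 7.1.1.

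3. **Section 9 with Section 5.6.** Reconcile the window with its six-month rationale and with continued follow-up, so that AE recording runs at least to the month-24 visit for everyone still followed, including early stoppers and those never dosed.

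4. **Sections 11 and 14.2 with Sections 9 and 9.2.** Reconcile them so that safety follow-up continues after early termination.

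The cost is protocol wording and possibly one telephone check-in per participant using the existing proforma. If the sponsor chooses to add month-6 tests to Table 5, that is a further visit cost; keeping the difference under item 2 needs no new procedures.
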